15.1.2 Adverse Events Leading to Discontinuation of Study Treatment

The frequency (number and percentage) of participants with each of the following will be presented for TEAEs leading to temporary/permanent discontinuation of each treatment of the combination or to the combination itself:

- TEAEs leading to discontinuation of Avelumab only by SOC and PT
- TEAEs leading to discontinuation of Axitinib only by SOC and PT
- TEAEs leading to discontinuation of Avelumab + Axitinib by SOC and PT
- Serious TEAEs leading to discontinuation of Avelumab only by SOC and PT
- Serious TEAEs leading to discontinuation of Axitinib only by SOC and PT
- Serious TEAEs leading to discontinuation of Avelumab + Axitinib by SOC and PT
- Avelumab related TEAEs leading to discontinuation of Avelumab only by SOC and PT
- Axitinib related TEAEs leading to discontinuation of Axitinib only by SOC and PT
- Related TEAEs leading to discontinuation of Avelumab + Axitinib by SOC and PT

- TEAEs (NCI-CTCAE [version 5.0]) Grade ≥ 3 leading to discontinuation of Avelumab only by SOC and PT
- TEAEs (NCI-CTCAE [version 5.0]) Grade ≥ 3 leading to discontinuation of Axitinib only by SOC and PT
- TEAEs (NCI-CTCAE [version 5.0]) Grade ≥ 3 leading to discontinuation of Avelumab + Axitinib by SOC and PT.

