Importantly, these clinical trials demonstrated that increased efficacy offered by these treatments was paralleled by acceptable safety profile. Treatment-related adverse events (TRAEs)  $\geq$  Grade 3 occurred in 46% of patients treated with Nivolumab plus Ipilimumab, 62.9% of patients treated with Pembrolizumab plus Axitinib and in 56.7% of patients treated with Avelumab plus Axitinib compared to 55.4% to 63.0% of patients receiving Sunitinib. TRAEs  $\geq$  Grade 3 occurred in  $\geq 10\%$  of patients were increased lipase levels among patients receiving Nivolumab plus Ipilimumab (10.0%), hypertension, and increased alanine aminotransferase levels in patients treated with Pembrolizumab plus Axitinib (22.1% and 13.3%, respectively), and hypertension in patients treated with Avelumab plus Axitinib (25.6%). Death due to toxicity of trial treatment was documented in 1.5% of patients treated with Nivolumab plus Ipilimumab, 0.9% of patients receiving Pembrolizumab plus Axitinib and 0.7% of patients treated with Avelumab plus Axitinib. About 22%, 10.7%, and 7.6% of patients treated with Nivolumab plus Ipilimumab, Pembrolizumab plus Axitinib, and Avelumab plus Axitinib, respectively, discontinued both study drugs due to TRAEs ([Rini 2019b](#)).

Furthermore, therapy modifications were frequent across the studies. For instance, delays in administration of Nivolumab and Ipilimumab occurred in 58% and 27% of patients, respectively ([Motzer 2018](#)), while 69.9% of patients had interruption of either Pembrolizumab or Axitinib ([Rini 2019a](#)). Axitinib dose was reduced in 20.3% of patients co-treated with Pembrolizumab and in 42.2% of patients co-treated with Avelumab ([Rini 2019a, Motzer 2019](#)). High doses of glucocorticoids for management of immune-related adverse events (AEs) were required by 35% of patients on Nivolumab plus Ipilimumab and only by 11.1% of patients on Avelumab plus Axitinib therapy ([Motzer 2018, Motzer 2019](#)). Among patients treated with Avelumab plus Axitinib, 38.2% had any grade pre-specified immune-related AEs, which were most frequently immune-related thyroid disorders (24.7% of patients) ([Motzer 2019](#)). In 9.0% of patients, these immune-related AEs were of  $\geq$  Grade 3 ([Motzer 2019](#)).

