### **Safety and tolerability:**

- Frequency and nature of all-cause AEs according to Medical Dictionary for Regulatory Activities (MedDRA) system organ class (SOC) and preferred term (PT) that occurred from the index date up to 90 days post discontinuation of Avelumab plus Axitinib or completion of the 24 months (i.e., end of the study) follow-up from the index date, whichever occurs first
- Frequency of all-cause AEs by maximum Common Terminology Criteria for Adverse Events (CTCAE) grade that occurred from the index date up to 90 days post discontinuation of

Avelumab plus Axitinib or completion of the 24 months (i.e., end of the study) follow-up from the index date, whichever occurs first

- Frequency of all-cause AE  $\geq$  Grade 3 leading to discontinuation of Avelumab plus Axitinib summarized by MedDRA SOC and PT
- Duration of Avelumab plus Axitinib therapy among patients who discontinued the study drug due to all-cause AEs  $\geq$  Grade 3
- Time to onset of all-cause AEs defined as the time interval from the index date to the onset of AE
- Duration of all-cause AEs defined as the time interval between the onset and resolution of AE
- Outcome of all-cause AEs: resolved, resolving, not resolved, resolved with sequelae, fatal, unknown
- Percentage of patients with therapy modifications due to AE related to Avelumab plus Axitinib therapy (e.g., therapy interruptions and reductions of infusion rate for Avelumab, therapy interruptions, and dose reductions for Axitinib)
- Frequency and type of medical intervention or medications used for the management of AE related to Avelumab plus Axitinib therapy (e.g., use of corticosteroids, antihypertensive therapy, treatment for thyroid dysfunction, measures to decrease hemoglobin, and hematocrit)
- Percentage of patients receiving later-line therapy and frequency distribution of later-line therapy regimes among patients progressing on Avelumab plus Axitinib including the names of medications of monotherapy/combination treatment used in second-line and third-line therapy
- Time to second-line therapy initiation is defined as the time from Avelumab plus Axitinib therapy discontinuation to the initiation of second-line therapy

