e The MSKCC risk score is based on 5 independent risk factors: low Karnofsky performance status (KPS), low hemoglobin level, high serum lactate dehydrogenase, high corrected serum calcium level, and time from diagnosis to the initiation of systemic therapy of less than 1 year (Heng 2013). The MSKCC risk score categorizes patients into 3 risk groups: 0 (low risk), 1 or 2 (intermediate risk), and  $\geq 3$  (high risk).

f The IMDC risk score is based on data of patients with metastatic RCC treated with targeted therapies and includes 6 risk factors: low KPS, low hemoglobin level, high neutrophil count, high platelet count, high corrected serum calcium level, and time from diagnosis to the initiation of systemic therapy of less than 1 year (Heng 2013). The IMDC risk score categorizes patients into 3 risk groups: 0 (low risk), 1 or 2 (intermediate risk), and  $\geq 3$  (high risk).

g All patients will be asked to fill HRQoL data available as ePRO questionnaires at the index date and at every third cycle of Avelumab treatment (intervals of about 6 weeks) thereafter, until the end of treatment or end of 24 months of study follow-up period, whichever occurs first.

h Avelumab plus Axitinib therapy: data on dose at regular follow-up visits, therapy modifications (change in dose) due to AE, temporary interruption, and treatment discontinuation will be collected upon availability.

i Treatment response includes data on complete response, partial response, stable disease, or progressive disease defined as per RECIST version 1.1. Data on treatment response will be collected upon availability.

j Information on treatment used for the management of AE related to Avelumab plus Axitinib therapy such as use of corticosteroids, antihypertensive therapy, treatment for thyroid dysfunction, measures to decrease hemoglobin, and hematocrit.

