### 9.7.3 Statistical Methods

Patient demographics, medical and cancer history, MSKCC and IMDC risk group, and concomitant medications will be summarized with appropriate descriptive statistics in the analysis set overall.

Medications will be summarized according to the WHO-DD, considering the first digit of the Anatomical Therapeutic Chemical (ATC) classification system (anatomic category) and the first 3 digits of the ATC class (therapeutic category). Multiple occurrences of the same drug in the same patient will be counted only once in the tables.

Recorded medications will be classified into the following groups:

- Prior medications are those that the patient took and discontinued prior to the index date
- Concomitant medications are those that the patient continued or started on or after the index date

- Medications used for the management of AE related to Avelumab plus Axitinib therapy on or after the index date
- Medications used as second-line or third-line therapy after the index date

The exposure will be analyzed descriptively by means of summary of treatment duration in weeks or months, reasons for dose reduction or temporary interruption, number of patients with permanent discontinuation, and reason for permanent discontinuation.

- The primary analysis will include:
  - OS rate (percentage of patients who are alive) at 12 months after the index date with the 95% CI
- The secondary analysis will include:
  - OS rate (percentage of patients who are alive) at 24 months after the index date with the 95% CI
  - OS will be estimated by the Kaplan-Meier method. The percentage of censored patients will also be reported. Median event time will be reported, along with 25th and 75th percentiles
  - Summary of absolute and relative frequencies of ORR and DCR up to 24 months after the index date together with the 95% CI
  - DoR, PFS, and PFS2 at 24 months after the index date will be estimated by the Kaplan-Meier method. The percentage of censored patients will also be reported. Median event time will be reported, along with 25th and 75th percentiles. Percentage of patients experiencing event or being event-free at applicable timepoints will also be reported along with the corresponding two-sided 95% CIs
  - There will be subgroup analyses for the primary outcome and selected secondary outcomes (OS, PFS, and PFS2 at 24 months and DCR up to 24 months) based on:

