    - ECOG performance status at baseline (0-1, > 1)
    - IMDC risk group (low, intermediate, high)
    - MSKCC risk group (low, intermediate, high)
    - RCC histopathology (clear cell, sarcomatoid, others)
    - PD-L1 (±) status
    - Age group (< 65, 65-75, and > 75 years)
    - Concomitant autoimmune disease (yes, no)
    - Prior nephrectomy (yes, no)

Further subgroup analysis will be defined in the IAP.

---

Safety analysis will be performed on AEs incidence tables, presented by MedDRA SOC and PT, and the number and percentage of patients experiencing an event. Multiple occurrences of the same event in the same patient will be counted only once in the tables.

Summaries of AEs will include:

- The overview of AEs, summarizing number (%) of patients with any:
  - AEs
  - SAEs
  - National Cancer Institute - Common Terminology Criteria for Adverse Events (NCI-CTCAE) (version 5.0) AEs  $\geq$  Grade 3
  - Related AEs
  - AEs leading to permanent treatment discontinuation
  - AEs leading to death
- Summary of AEs by SOC and PT
- Summary of SAEs by SOC and PT
- Summary of NCI-CTCAE (version 5.0) AEs  $\geq$  Grade 3 by SOC and PT
- Summary of related AEs by SOC and PT
- Summary of related AEs (NCI-CTCAE [version 5.0])  $\geq$  Grade 3 by SOC and PT
- Summary of AEs leading to permanent treatment discontinuation by SOC and PT
- Summary of AEs (NCI-CTCAE [version 5.0])  $\geq$  Grade 3 leading to permanent treatment discontinuation by SOC and PT
- Summary of potential signs and symptoms of immune-related AEs
- Summary of AEs leading to death by SOC and PT

Exposure among the patients who discontinued the study drug due to all-cause AEs  $\geq$  Grade 3 will be summarized as per appropriate statistics.

Percentage of patients with therapy modifications due to related AEs (e.g., therapy interruptions and reductions of infusion rate for Avelumab, therapy interruptions and dose reductions for Axitinib) and frequency and type of medical intervention or medications used for the management of related AEs (e.g., use of corticosteroids, antihypertensive therapy, treatment for thyroid dysfunction, and measures to decrease hemoglobin and hematocrit) will be presented.

Percentage of patients receiving later-line therapy (e.g., second-line therapy, third-line therapy) and frequency distribution of later-line therapy regimes among patients progressing on Avelumab plus Axitinib therapy will be presented.

---

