15.1.1 All Adverse Events

The following tables will be presented:

- Overview of TEAEs, summarizing number (%) of patients with any:
 - TEAEs
 - Related TEAEs (overall and to Avelumab or Axitinib)
 - Serious TEAEs
 - Related (overall and to Avelumab or Axitinib) serious TEAEs
 - National Cancer Institute - Common Terminology Criteria for Adverse Events (NCI-CTCAE) (version 5.0) TEAEs Grade ≥ 3
 - Related (overall and to Avelumab or Axitinib) NCI-CTCAE TEAEs Grade ≥ 3
 - TEAEs leading to death
 - Related (overall and to Avelumab or Axitinib) TEAEs leading to death
- Overview of TEAEs leading to discontinuation
- Summary of TEAEs by SOC and PT
- Summary of serious TEAEs by SOC and PT
- Summary of related (overall and to Avelumab or Axitinib) TEAEs by SOC and PT
- Summary of NCI-CTCAE (version 5.0) TEAEs Grade ≥ 3 by SOC and PT
- Summary of TEAEs leading to death by SOC and PT
- Summary of serious related (overall and to Avelumab or Axitinib) TEAEs by SOC and PT
- Summary of serious NCI-CTCAE (version 5.0) TEAEs Grade ≥ 3 by SOC and PT
- Summary of serious TEAEs leading to death by SOC and PT
- Summary of related (overall and to Avelumab or Axitinib) TEAEs NCI-CTCAE (version 5.0) Grade ≥ 3 by SOC and PT
- Summary of related (overall and to Avelumab or Axitinib) TEAEs leading to death by SOC and PT

- Summary of TEAEs NCI-CTCAE (version 5.0) Grade ≥ 3 leading to death by SOC and PT
- Summary of potential signs and symptoms of immune-related TEAEs.

Exposure (exposure duration [days and cycles when applicable] and cumulative dose [milligrams]) among the patients who discontinued the study drugs due to all-cause TEAEs Grade ≥ 3 will be summarized as per appropriate statistics.

Percentage of patients with therapy modifications due to AEs related to Avelumab and/or Axitinib (eg, therapy interruptions and reductions of infusion rate for Avelumab, therapy interruptions and dose reductions for Axitinib) and frequency and type of medical intervention or medications used for the management of related AEs (eg, use of corticosteroids, immunosuppressants, or hormonal therapy) will be presented.

Percentage of patients receiving later-line therapy (eg, second-line therapy, third-line therapy) and frequency distribution of later-line therapy treatments among patients progressing on Avelumab plus Axitinib therapy will be presented.

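### SAP 15.1.2 does not separate temporary from permanent discontinuation in its TEAE tables, although Protocol 9.7.3 specifies permanent discontinuation

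*SAP*

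**What the plan says.** SAP 15.1.2 opens with a scope statement covering "TEAEs leading to temporary/permanent discontinuation of each treatment of the combination or to the combination itself". The tables listed below it use the unqualified word, for example "TEAEs leading to discontinuation of Avelumab + Axitinib by SOC and PT". SAP 15.1.1 adds a summary that is also unqualified: "Overview of TEAEs leading to discontinuation". This is Table 8.3.1.2 in the list of primary-analysis outputs.

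Protocol 9.7.3 includes "Summary of AEs leading to permanent treatment discontinuation by SOC and PT", and uses the same term in the AE overview and in the Grade 3 or higher summary. The outcome list in Protocol 9.1.2.2 is looser: it refers to Grade 3 or higher AEs "leading to discontinuation of Avelumab plus Axitinib summarized by MedDRA SOC and PT", without the word permanent.

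The protocol keeps the two concepts apart elsewhere. Its exposure analysis covers "reasons for dose reduction or temporary interruption, number of patients with permanent discontinuation, and reason for permanent discontinuation". The footnote to its Schedule of Assessments names them as separate items: "temporary interruption, and treatment discontinuation will be collected upon availability".

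**The concern.** An AE that makes a patient stop a drug for good and an AE that makes a patient pause and resume are different tolerability results. The protocol reports the first as discontinuation and treats the second as a therapy modification. A programmer following SAP 15.1.2 literally could flag both as discontinuation and fill all 12 tables from that flag.

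Three things are at stake.

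- **Protocol tables.** The permanent-only SOC/PT and Grade 3 or higher tables that the protocol asks for would not be produced.
- **Consistency within the report.** Immune-related and infusion-related events would be counted on permanent discontinuation and all TEAEs on a wider definition, so the two could not be set side by side.
- **A secondary objective.** SAP section 5 points the objective on time to discontinuation for Grade 3 or higher AEs to section 15.1.2. If the same flag picks the patients for the exposure summary in 15.1.1, a patient who paused for a Grade 3 event and resumed would enter it. Under SAP section 13 exposure runs to the last treatment date, so that patient's duration would end at a dose unrelated to the event.

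**Working it through.** The documents give no figure for this point, so the check is a comparison of text.

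| Place | Scope used |
|---|---|
| Protocol 9.7.3: AE overview, SOC/PT summary, Grade 3 or higher SOC/PT summary | Permanent, in all three |
| Protocol 9.7.3: exposure | Temporary interruption and permanent discontinuation named separately |
| Protocol Table 1, footnote on study therapy | Collected as separate items |
| Protocol 9.1.2.2: Grade 3 or higher outcome | Discontinuation, unqualified |
| SAP 15.1.2: opening sentence | Temporary/permanent |
| SAP 15.1.2: listed tables | Discontinuation, unqualified |
| SAP 15.1.1: overview | Discontinuation, unqualified |
| SAP 15.1.1: therapy modifications | Interruptions placed here, for related AEs only |
| SAP 15.2.3: irAEs and IRRs | Permanent |
| SAP section 7: changes from protocol | ORR/DCR timing only |

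**Number of tables.** Three drug scopes (avelumab only, axitinib only, both) times four event types (all, serious, related, Grade 3 or higher) gives 3 × 4 = 12. None of the 12 titles carries temporary or permanent as a qualifier.

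**Direction.** Patients with any discontinuation under the pooled scope = patients with a permanent discontinuation + patients with only a temporary one. The second term cannot be negative, so the overall count can only rise. With about 100 patients planned (Protocol 9.5), each added patient moves a percentage by about 1/100, or 1 percentage point. Pooling can also shift events between rows: an AE that stopped axitinib for good and only paused avelumab would move from the axitinib-only row to the row for both.

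**Size.** This would need the number of patients with a TEAE that led only to a temporary stop. Neither document gives an AE-related interruption rate for avelumab plus axitinib, so no estimate follows.

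**The case against.** The best defence is that pooling is inferred. Temporary/permanent may mean that each kind is tabulated, just as the same sentence goes on to each drug and the combination. The 12 entries name table topics and no table shells are included. This stands in part: pooling is the natural reading but not the only one, which is why the point says that such events can be counted, not that they will be. It does not remove the problem, because the SAP lists one set of tables and gives no instruction to split them.

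Second, permanent stops are reported elsewhere. SAP 10.1 counts participants who discontinued each drug by main reason, and lists those who stopped permanently. True, but these outputs are not by SOC/PT or by grade, so they do not replace the protocol's tables.

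Third, Protocol 9.1.2.2 and the endpoint in SAP section 5 say only discontinuation. Also true: the word permanent rests on Protocol 9.7.3. That section, however, applies it to the same Grade 3 or higher SOC/PT summary, and 9.1.2.2 itself lists interruptions separately, as therapy modifications.

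A reader might go further and infer a several-fold inflation from the Rationale and Background. There, for another combination, "69.9% of patients had interruption of either Pembrolizumab or Axitinib", while 10.7% stopped both drugs for treatment-related AEs (69.9/10.7 = 6.5). The documents do not support that inference. The first figure is for either drug with no cause stated; the second is for both drugs and related events only. Neither comes from avelumab plus axitinib, and an either-drug rate matches no row of SAP 15.1.2.

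**Conclusion.** The SAP and the protocol conflict on the scope of the discontinuation tables, and the SAP does not declare the difference. Followed literally, SAP 15.1.2 yields no permanent-only SOC/PT or Grade 3 or higher table. Any pooling raises the overall count of patients with a discontinuation and makes it inconsistent with Protocol 9.7.3 and with SAP 15.2.3. The size is unknown.

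The conclusion assumes that the opening sentence of 15.1.2 governs all 12 tables. The effect on the Grade 3 or higher exposure summary further assumes that it uses the same flag. All affected outputs are descriptive and the primary endpoint is untouched. Even so, the overview is due with the primary analysis, so the wording should be settled before that database lock.

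**What to change.** - In SAP 15.1.2, restrict the 12 tables to TEAEs with permanent discontinuation of avelumab, axitinib or both, as in Protocol 9.7.3.
- Apply the same rule to the overview (Table 8.3.1.2) and to the exposure summary for Grade 3 or higher discontinuations in SAP 15.1.1.
- Present TEAEs leading to temporary interruption in separate tables. The existing therapy-modification summary does not cover this fully, because it is limited to related AEs.
- Add the word permanent to the Grade 3 or higher endpoint in SAP section 5, so that the objective and its tables agree.

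No new data should be needed: Protocol 11.4 has the action taken with study drug recorded for each AE. The eCRF is not among the documents, so confirm that this field distinguishes interruption from permanent withdrawal for each drug. The cost is a change of SAP wording and a few extra descriptive tables. The change concerns tabulation only and touches no rule on treatment.

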15.2 Deaths, Other Serious Adverse Events, and Other Significant Adverse Events

15.2.1 Deaths

The following summaries for the deaths will be reported in a table:

- Number and percentages of deaths
- Number and percentages of deaths due to COVID-19 (identified based on specification collected when reason for death corresponds to “Event unrelated to study treatment”)
- Number and percentages for each primary reason of death (percentage calculated using the number of deaths as denominator):
 - Progressive disease and/or disease related condition
 - Event unrelated to study treatment
 - Event related to Avelumab
 - Event related to Axitinib
 - Unknown.

A listing with the following columns will be presented:

- Patient number
- Age (yrs.)/ Sex/ Weight (kilograms)
- First dose date, last dose date, dose in milligram or dose not administered for Avelumab and Axitinib
- Date of death
- Primary cause of death
- If event unrelated to study treatment, specify
- Fatal AE
- Period

- irAE or IRR flag

15.2.2 Serious Adverse Events

The following overall frequency tables will be prepared for serious AEs:

- Incidence of serious AEs by SOC and PT
- Incidence of related serious AEs by SOC and PT
- Incidence of serious NCI-CTCAE [version 5.0]) Grade ≥ 3 by SOC and PT
- Incidence of serious AEs leading to death by SOC and PT

The listings of serious adverse events (SAEs) will also be provided with the relevant information:

- Patient number
- Age (yrs.)/ Sex/ Weight (kilograms)
- Start date/ End date
- Seriousness criteria
- Is a TEAE? (Yes/No)
- Relationship with Avelumab (Not Related/ Related)
- Relationship with Axitinib (Not Related/ Related)

For the seriousness criteria report all that apply: Results in death, Is life-threatening, Requires/prolongs hospitalization, Persistent/significant disability/incapacity, Is a congenital anomaly/birth defect, Other medically important condition.

